13.5.4.2 Pregnancy

The number of pregnancies in each group during the study period is collected, and the final pregnancy results are classified and described.

13.5.4.3 Vital Signs Assessment

A descriptive analysis of vital sign measurements and changes of the measurements after treatment as compared to baseline is performed by visits and treatment groups. Meanwhile, the abnormal values of vital signs are tabulated.

13.6 Registration and Declaration Strategy

Initial analysis

After all subjects complete a 99-day safety and efficacy evaluation after administration (based on the serological results on Study Days 1, 4, 8, 15, 43 and 99), the first analysis will be conducted, and a statistical analysis report and clinical research report will be formed and submitted to the National Medical Products Administration (NMPA) for review.

Secondary analysis

After all subjects complete a one-year safety and efficacy evaluation after administration, the secondary analysis will be conducted, and a statistical analysis report and clinical research report will be formed and submitted to the National Medical Products Administration (NMPA) as a supplement, and also to the U.S. Food and Drug Administration (FDA) for review.

13.7. Data and safety monitoring board (DSMB)

A DSMB will be convened in this trial. The DSMB's purpose is to monitor the death and rabies cases during the entire study period.

The DSMB's composition and working contents will be specified in the DSMB charters.

13.8 Per Protocol Adjudication Board (PPAB)

The Sponsor will create the Per-protocol Adjudication Board whose duty will be to review data and confirm the rabies cases in the study. The confirmed rabies events is one of the primary endpoints of the study. In case any rabies event in the SYN023 arm, the primary endpoint will be reached for the study failure. In case of lab-confirmed or clinically suspected rabies cases during the study, the study enrollment would be suspended and detailed information would be submitted to PPAB for reviewing and confirmation, so that PPAB can confirm the diagnosis of rabies cases. If a confirmed case of rabies occurs in the SYN023 arm (as in the per protocol set and in the SYN023 group), the clinical trial will be permanently discontinued by PPAB on a written notice. If the rabies case occurred in the control group or in the SYN023 group but PPAB deems that the case was caused by a violation of the study protocol, The study will not

be stopped by the rabies case. The operating procedures in violation of the protocol include:

- Received the incorrect Study Drug
- Received the incorrect dose ($\pm 20\%$) of Study Drug
- Fail to comply with Category III rabies exposure.
- Failed to complete the scheduled rabies vaccinations through the study
- Are discovered to lack adequate prophylactic treatment of all exposure sites
- Are discovered to be injured by animal other than those listed
- Are discovered to have an interval > 24 hours from rabies exposure to the start of Informed Consent
- Are discovered to have RVNA ≥ 0.1 IU in serum obtained at Study Day 1
- Receives prohibited treatment during the trial
- Are found not to have a modified WHO Category 3 exposure
- Second high risk animal bite or contact requiring PEP

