Objectives	
Primary objectives:
 
 ● To demonstrate the Geometric mean RVNA Concentration for SYN023 recipients is superior to the geometric mean RVNA concentration for HRIG recipients on Study Day 8, AND ● There are no probable or confirmed cases of rabies in SYN023 recipients. 
Secondary objectives:
 
 ● To demonstrate the Geometric mean RVNA Concentration for SYN023 recipients is superior to the geometric mean RVNA concentration for HRIG recipients on Study Day 4; ● To demonstrate that the geometric mean RVNA AUEC₁₋₁₅ for SYN023 is

	
superior to the geometric mean RVNA AUEC₁₋₁₅ for HRIG;
 
 ● To demonstrate that the Study Day 99 geometric mean RVNA concentration for SYN023 recipients is not inferior to the geometric mean RVNA concentration for HRIG recipients; ● To demonstrate that the percentage of subjects with RVNA concentration ≥ 0.5 IU/mL on Study Day 99 in SYN023 recipients is not inferior to the percentage of recipients with RVNA concentration ≥ 0.5 IU/mL for HRIG; ● To describe the ratio of the geometric mean concentrations of RVNA at each time point in SYN023 recipients divided by the geometric mean concentrations of RVNA in HRIG recipients in the per-protocol and as-treated populations; ● To describe the percentage of RVNA concentration ≥ 0.5 IU/mL at each time point for SYN023 and HRIG recipients in the per-protocol and as-treated populations; ● To describe any effect of increasing BMI on SYN023 and RVNA concentrations; ● To evaluate the safety of SYN023 compared to HRIG. 													
	
Overall Design:
 
This is a Phase III, randomized, blinded, and active controlled study of SYN023 compared with a China licensed HRIG for PEP of patients who have been confirmed to have met all inclusion/exclusion criteria for their treatment group.
													

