2. STUDY OBJECTIVES

2.1 Primary Objective

- To demonstrate that the GMC of RVNA in the "SYN023 + rabies vaccine" group is superior to that of the "HRIG + rabies vaccine" group on Study Day 8 after administration;
- To demonstrate that during the research period, the group administered with SYN023 combined with a rabies vaccine has no probable or confirmed case of rabies.

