- 3) Any mucous membrane is contaminated by animal saliva (such as being licked)
- 4) Exposure to a bat (post-exposure prophylaxis should be considered after any contact with a bat unless there is no bite, scratch or exposure of any mucous membrane)

Note: Bites on the head, face, neck, hands and external genital organs are classified as Category III Exposure.

WHO's Definition of Rabies:

Clinical case: refers to a case with acute neurological syndrome (such as encephalitis), which is mainly manifested as hyperactivity (in the case of furious rabies) or paralysis syndrome (in the case of paralytic rabies). If no intensive care is provided, a patient usually falls into a coma and then dies within 7-11 days after the occurrence of the first symptom, which is usually caused by respiratory and circulatory failure. A patient can be diagnosed with rabies when one or more of the following laboratory criteria can be met:

- A. The presence of rabies viral antigens;
- B. The rabies virus is detected with the cell culture method or laboratory animal inoculation;
- C. There are rabies virus-specific antibodies in the cerebrospinal fluid or serum of an unvaccinated person;
- D. Rabies Viral nucleic acid is detected in any biological sample or sample for autopsy (such as brain biopsy sample, skin, saliva, and concentrated urine) with molecular biological methods.

WHO's Classification of Rabies Cases:

- ① Suspected case: refers to a case that satisfies the definition of clinical case;
- ② Probable case: refers to a suspected case with a reliable medical history of contact with any suspected animal infected with the rabies virus;
- ③ Confirmed case: refers to a suspected or probable case that is proved to be infected based on the lab test result.

In the absence of exposure to any host animal or clinically suspected encephalitis symptoms, a case can also be determined as a confirmed case if the diagnosis is sufficiently supported by the lab test result.

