7. STUDY ENDPOINTS

7.1 Primary Endpoints

- GMC of RVNA on Day 8 after administration.
- The incidence and survival rate of rabies in subjects within 99 days and 1 year after administration.

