9.2 Inclusion Criteria

- 1) Is age 18 years, on Study Day 1 with legal identification documents, and plan to live in the local administration area during the study;
- 2) Category III rabies exposure within 24 hours before Study Drug receipt ;
- 3) Completed written informed consent process, and signed the informed consent forms;
- 4) Subjects with the ability to understand the study procedure. And agreed to complete all follow-ups;
- 5) Female subjects are not in pregnancy (with negative results of urine pregnancy tests before vaccination) and are not in the period of breast feeding, and agree to avoid pregnancy within 6 months after administration;
- 6) Those who have an armpit temperature $\leq 37.0^{\circ}\text{C}$.

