1.1 Study Objectives

1.1.1 Primary Objectives

- To demonstrate the superiority of SYN023 plus Rabies Vaccine over Human Rabies Immune Globulin (HRIG) plus Rabies Vaccine as measured by the geometric mean concentration (GMC) of rabies virus neutralizing activity (RVNA) on Study Day 8.
- There are no cases of probable or confirmed rabies in SYN023 recipients. .

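### The rabies co-primary is stated at inconsistent case levels: probable or confirmed in the objectives, confirmed in the adjudication text, and unspecified in the endpoint and analysis text

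*Protocol*

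**What the plan says.** **Objectives.** The Protocol synopsis (Objectives) states: "There are no probable or confirmed cases of rabies in SYN023 recipients". It joins this to Day 8 RVNA superiority with a capitalised AND. Protocol 2.1 requires that "the group administered with SYN023 combined with a rabies vaccine has no probable or confirmed case of rabies", and SAP 1.1.1 agrees: "There are no cases of probable or confirmed rabies in SYN023 recipients".

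**Endpoints.** Protocol 7.1 lists "The incidence and survival rate of rabies in subjects within 99 days and 1 year after administration". The synopsis (Endpoints) and SAP 1.2.1 are equivalent. None names a level of diagnostic certainty.

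**Analysis.** Protocol 13.5.3 and SAP 3.2.1.2 describe incidence and survival, with no case level and no success rule.

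**Adjudication.** Protocol 13.8, repeated in the synopsis row on the Per Protocol Adjudication Board (PPAB), uses several levels within one paragraph:
- the endpoint: "The confirmed rabies events is one of the primary endpoints of the study";
- study failure: any rabies event in the SYN023 arm;
- suspension of enrollment and referral to the PPAB: a laboratory-confirmed or clinically suspected case;
- permanent discontinuation: a confirmed case in the SYN023 arm and the per protocol set.

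**Definitions.** Protocol 2.3 defines a suspected case as one meeting the clinical case definition. It continues: "Probable case: refers to a suspected case with a reliable medical history of contact with any suspected animal infected with the rabies virus". A confirmed case is a suspected or probable case with laboratory proof.

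**The concern.** The rabies objective tolerates no case in the SYN023 arm, so a single subject decides it, and the synopsis makes it a condition of success alongside the RVNA comparison. An endpoint of this kind needs its event defined before any event occurs. Here the objective and the adjudication text give different events, and the text that should settle the matter (endpoint list, analysis section, SAP) is silent.

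If a borderline case arose, the reading would have to be chosen after the case was known. Timing adds to this. Protocol 8.2.5 unblinds after Day 99 follow-up and database lock, while rabies follow-up runs to one year. Follow-up investigators stay blinded, but the sponsor and statisticians sign the unblinding documents. A late case could therefore be interpreted with the treatment arm already known to them.

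**Working it through.** **1. Is there a plan figure to reproduce?** No. Protocol 13.1 and 13.3 and SAP 1.3.3 and 2.4 set hypotheses, margins and sample sizes for RVNA only. The check is therefore to apply each wording as a decision rule to the same patient.

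**2. The test case.** A SYN023 recipient has an illness that meets the clinical case definition, a reliable history of contact with a suspected infected animal, and no laboratory proof. Under Protocol 2.3 this is probable and not confirmed.

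**3. Result under each wording.**

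| Text | Level stated | Result for the test case |
|---|---|---|
| Objectives (synopsis; Protocol 2.1; SAP 1.1.1) | probable or confirmed | objective fails |
| Endpoint lists (synopsis; Protocol 7.1; SAP 1.2.1) | none | undetermined |
| Analysis (Protocol 13.5.3; SAP 3.2.1.2) | none | undetermined |
| 13.8, endpoint sentence | confirmed | not an endpoint event, taking confirmed as defined in 2.3 |
| 13.8, failure sentence | any rabies event | undetermined: fails if a probable case counts as an event |
| 13.8, discontinuation rule | confirmed, per protocol set | not triggered |
| 13.8, suspension and referral | laboratory-confirmed or clinically suspected | triggered |

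The objectives and the endpoint sentence disagree outright. The remaining texts do not resolve the disagreement.

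**4. Could such a case arise?** Yes. Protocol 11.11.2 and 14.2 collect autopsy results only where an autopsy took place. One of the four laboratory criteria in 2.3, specific antibody, applies only to an unvaccinated person, and every subject is vaccinated from Day 1. The supplied text describes no sampling procedure for a suspected case.

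**5. How often would suspected also mean probable?** Entry requires "Category III rabies exposure within 24 hours before Study Drug receipt", so every subject has a documented exposure and most suspected cases would probably also be probable. The share is unknown. Protocol 2.3 lets exposure to an animal of uncertain host status qualify, whereas probable needs reliable contact with a suspected infected animal. SAP 3.1.3 lists the animal causing the wound, but not its infection status.

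**6. Population.** The objectives cover SYN023 recipients. The discontinuation rule is limited to the per protocol set, and SAP 2.2 and 3.2 make that set primary for efficacy endpoints. Membership requires completing the vaccine course, so the two populations can differ for exactly the subject in question.

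**7. Scale, on assumed rates only.** With n = 750 and an assumed one-year per-subject risk p of a probable, unconfirmed case, P(at least one) = 1 − (1 − p)^750:
- p = 0.001%: 0.7%
- p = 0.01%: 7.2%
- p = 0.1%: 52.8%

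The documents give no value for p. The spread shows only that they cannot settle how likely the event is.

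**The case against.** **The failure sentence does not say confirmed.** A reader might infer that study failure counts confirmed cases only. The text does not support that: the sentence refers to any rabies event and can be read in line with the objectives. This stands. It means the two rules can give opposite conclusions, not that they must. It also adds another wording to the same paragraph.

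**Confirmed may mean confirmed by adjudication.** Section 13.8 uses a separate term for laboratory-confirmed cases and sends both those and clinically suspected cases to the PPAB for confirmation. On that reading an adjudicated case without laboratory proof could count. It would therefore be too strong to say that every case without a sample is missed under 13.8. But 2.3 defines confirmed by laboratory result and 13.8 gives no other definition, so the ambiguity remains.

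**Not every encephalitis is probable rabies.** A reader might infer from the entry criterion that any acute encephalitis in this trial would count. The clinical definition is narrower (a syndrome mainly of hyperactivity or paralysis, usually progressing to coma and death), and the contact history must be reliable. This stands. A false-failure probability that counted all background encephalitis would be an upper-end illustration on an incidence the documents do not give.

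**Some case-handling text is not available.** Protocol 8.2.4 refers to a section 14.3 that is absent from the supplied text, and the data and safety monitoring board charter is a separate document. Either could add procedure. Neither would remove the conflict between the passages quoted here.

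**Conclusion.** The inconsistency is in the text and needs no assumption: the objectives count probable or confirmed cases, the 13.8 endpoint sentence counts confirmed cases, and the endpoint and analysis sections do not choose. Its size is one subject, because one probable, unconfirmed SYN023 case can fail the objective without being an endpoint event under 13.8. This rests on reading confirmed as Protocol 2.3 defines it. If confirmed means adjudicated, the rule is ambiguous rather than contradictory, and it still needs stating. The population mismatch is a second, separate gap in the same rule. The documents do not establish how likely such a case is, or that any particular wrong conclusion would follow.

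**What to change.** State one case level and one analysis population for the rabies co-primary. The objectives already contain both: PPAB-adjudicated probable or confirmed rabies, in all SYN023 recipients. Carry this into:
- the synopsis rows on endpoints and on the PPAB;
- Protocol 7.1 and 13.5.3;
- the endpoint and failure sentences of Protocol 13.8;
- SAP 1.2.1 and 3.2.1.2, stating that this endpoint is not restricted to the per protocol set.

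Have the PPAB classify every referred suspected case, while blinded, under the existing suspected, probable and confirmed definitions. Add one stated outcome, not rabies, for a case in which another diagnosis is established. A negative work-up without another diagnosis keeps the level that the existing definitions give it, so no new definition of probable is needed.

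The discontinuation passages in 13.8 and the synopsis must be reconciled with the chosen level and population. Which discontinuation rule is right is not decided here.

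**Cost.** Wording in the protocol, the SAP and the PPAB's procedures. Suspected cases already go to the PPAB under 13.8, and Protocol 13.4 already has it review blinded data. The small downside is that an unconfirmed case can count against SYN023, which the stated objective already requires. The change should be made before any case has to be classified.

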14. SAFETY MANAGEMENT

14.1 Safety Precautions

Clinical test shall be conducted at county-level and municipal-level medical institutions that are eligible for rabies vaccination. Before the initial of the trial, the Sponsor shall inspect the research site strictly according to the GCP, especially on the facilities complying with the Quality Management Guidelines for Clinical Trials for Vaccines (Trial) and to ensure the first-aid facility and equipment in emergency rooms are effective, the first-aid drugs are in valid period with the qualified and capable first-aid doctors. The Sponsor shall ensure that once an AE occurs, the subject could get timely treatment at the site. If emergency hospitalization is required, after the disease becomes stable, the subject could be sent to the assigned hospital by the ambulance vehicle of the site. The site shall sign the Green Channel Contracts with assigned local county or municipal-level general hospitals. The investigator shall notify the assigned hospital during the enrollment period, and make out qualified SOP for related personnel's duties, contact information, rescue measures and so on to ensure timely treatment of unexpected AEs and effective communication between the subject and the investigator, and further ensure a quick and timely report and handling of AEs. If the subject needs the emergent treatment after an SAE, the assigned hospital shall be able to provide green channel medical services, including treatment, hospitalization, and health care to ensure that the subject can be treated in a timely manner.

The Sponsor shall appoint the special personnel for monitoring of safety in clinical trial and the management of SAE. Both the Sponsor and the investigator shall establish SOPs for

the safety monitoring and SAE in clinical trial, and provide training for all relevant personnel. The monitoring and reporting of AEs in the vaccine clinical trial shall be performed by subjects, medical monitor and researchers at its time points evaluation and specific duties.

14.2 Detection and Collection of AEs

For the subjects with solicited and non-solicited AEs, the investigator shall ask whether they have received hospitalization, outpatient treatment, etc., for any reason, or taken drugs by themselves, and record such information.

The investigator shall remind the subjects to report AE in time during the training of subjects, always keep a vigilant eye on AEs, and investigate and deal with AEs in a timely manner.

When an AE occurs, the investigator is obliged to review all documents related to the event (e.g. progress notes and medical orders, laboratory reports and diagnosis reports), or arrange a clinical examination/test as requested by the Sponsor to clarify the nature and relevance of the SAE. If a subject is confirmed dead during the study period or the follow-up period, the investigator shall collect the final conclusion provided by the hospital regarding the subject, and also a copy of autopsy results, including histopathological results, if an autopsy is performed.

The investigator shall try to collect a complete copy of the medical history of the subject, but shall not replace the study record with medical history copy. Besides this, the investigator shall also record all information related to the SAE on the original record, eCRF, and SAE report page.

If medical records need to be disclosed for the purpose of medical identification, all contents that may reveal the identity of the subject shall be obscured before disclosure.

14.4 Reporting of SAEs

14.4.1 Reporting Time

After learning of SAE, the investigator shall make an initial report by filling in the SAE Report Form within 24 hours, and submit the form to the Sponsor by fax, email or web. Once received a SUSAR cases confirmed by the sponsor, the investigator shall submit related information to the EC in a timely manner.

Reporting Contents as following:

- 1) Types of report and reporting time (initial report, follow-up report, summary report and corresponding reporting time);
- 2) Information of subjects (initials, study number, date of birth, gender);
- 3) Information of reporter (name of the working medical institution and profession,

telephone, position/professional title of the reporter);

- 4) Information of suspected drugs (drug names in Chinese and English, registration classification and dosage form);
- 5) Study related information (clinical study approval number, clinical study classification, clinical indications);
- 6) Complications and treatment information (name of disease diagnosed, name, usage and dosage of drugs used);
- 7) Details of SAE (diagnosis name, time of occurrence, end time, laboratory test results, treatment process, outcome, measures taken against the experimental vaccine, the correlation with the experimental vaccine and so on);
- 8) Time of knowing by investigators;
- 9) Signature of investigators.

14.4.2 Sponsor

14.4.2.1 Suspected Unexpected Serious Adverse Reaction (SUSAR)

Sponsors should analyze and evaluate all SAEs reported from the investigator timely, including the severity, relatedness, and anticipation of the IMPs. The sponsor shall promptly report suspected and unexpected SAE to all investigators participating in the clinical trial, the Institutional Management Office, and the ethics committee (EC); The Sponsor shall report SUSAR to the drug regulatory authorities and the health authorities.

For other potential serious safety risk information, the sponsor should also report to the national center of drug evaluation as soon as possible.

14.4.2.2 Periodical Safety Updated Report (PSUR)

The sponsor should submit the PSUR to the CDE, all the researchers participating in the clinical trials, and EC in accordance with the requirements of the regulatory authorities and the EC. The PSUR shall include risk and benefit evaluation in the clinical trial.

